- To evaluate the superiority of romiplostim plus dexamethasone vs dexamethasone alone after 12 months (≥365 days) from treatment cessation, if data available, in patients with newly primary immune thrombocytopenia in terms of sustained response off any ITP treatment (12mSROT-30 and 12mSROT-50) from treatment cessation and without WHO grade 2 or more bleeding.
- To evaluate the superiority of romiplostim plus dexamethasone vs dexamethasone alone in terms of complete response (CR), response (R) global response (GR) and response within the target range (TR) at 6 months (Day 180), at 12 months (Day 365) from randomisation and End of study Visit (visit 12 months after the last dose of study treatment). We will evaluate them in the who trial cohort but also in a subgroup that excludes patients receiving any rescue treatment. Or an additional sensitivity analysis will exclude patients receiving rescue treatment.
- To compare the time to first response defined as the time from randomization to first response (R) in both arms. We will evaluate this in the total sample and in the absence of any rescue treatment.
- To compare the proportion of patients with early response (ER) and initial response (IR) in both arms.
- To compare the duration of platelet response assessed as: the maximum number of consecutive days with platelet response (CR, R, GR and TR) and, the total number of days along the study period with platelet response (CR, R, GR and TR) in both arms. We will evaluate them in the total sample and in the absence of any rescue treatment.
- To compare the time to loss of response (LoR) in patients who achieved response in both arms.
- To compare the proportion of patients requiring any rescue treatment along the study period in both arms

- To evaluate and compare proportion of treatment failure and time to treatment failure.
- To evaluate the safety and tolerability of study treatments in both arms.
- To compare the difference between study arms in the mean change in patients' bleeding
- To compare the change in patients' quality of life from baseline Day 1(the day of administration of the first dose of study medication) to 2 (Week 8), Month 6 (Day 180), Month 12 (Day 365) and End of study Visit (visit 12 months after the last dose of study treatment) assessed with SF-36 v2, FACIT-F and ITP-PAQ in both arms.
- To describe and compare healthcare resources use (HRU) and loss of productivity in both study arms.

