- To evaluate the difference between study arms in the proportion of patients with response within the target range (TR) at 6 months (Day 180), at 12 months (Day 365) from randomisation and End of study Visit (visit 12

months after the last dose of study treatment). We will evaluate this in the total sample and in the absence of any rescue treatment

- Definition of TR: platelet count between ≥30x10⁹/L and ≤400x10⁹/L.
- To evaluate the difference between study arms in the median time to first response defined as the time from randomization to first response (R) in the absence of any rescue treatment. We will evaluate this in the total sample and in the absence of any rescue treatment.
- To evaluate the difference between study arms in the proportion of patients with early response (ER) and initial response (IR).
 - Definition of ER: proportion of patients with platelet count higher or equal than 30x10⁹/L and at least doble than baseline at first week (Day 7) from randomisation.
 - Definition of IR: proportion of patients with platelet count higher or equal than 30x10⁹/L in the first month (Day 30) from randomisation.
- To compare the difference of means between study arms of the maximum number of consecutive days with platelet response (CR, R, GR and TR) along the study period. We will evaluate them in the total sample and in the absence of any rescue treatment
- To compare the difference of means between study arms of the total number of days with platelet response (CR, R, GR and TR) along the study period. We will evaluate them in the total sample and in the absence of any rescue treatment.
- To evaluate and to compare the proportion of patients who need rescue treatments and proportion and time to treatment failures
- To compare the time to loss of response (LoR) in patients who achieved response in both arms.
 - Definition of LoR: number of days from the first time the patient achieved a platelet count ≥30x10⁹/L until platelet count dropped below 30x10⁹/L measured on 2 occasions with more than 1 day apart or presence of bleeding
- To compare the difference between study arms in the proportion of patients requiring any rescue treatment along the study period.

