11. STATISTICAL CONSIDERATIONS

a. General considerations

The statistical analysis plan will be developed and finalized before database lock.

Descriptive statistics will be obtained for all variables: mean, median, standard deviation and range, Q1, Q3, and CI 95% for continuous variables, and frequencies and percentages for categorical variables.

Summary statistics will be provided by treatment groups for disposition, demographics, baseline characteristics, exposure to investigational product, adverse events, concomitant medication, labs and clinical outcome assessment data.

A Chi- square test or Fisher test if applicable will be used to compare categorical variables between groups. Time-to-event variables will be estimated by the Kaplan-Meier method from the randomisation. The log-rank test will be used to compare the survival curves. All the other endpoints will be compared between the two arms with appropriate statistical tests. All statistical tests will be two-sided with an α -level of 0.05.

b. Sample size

The primary endpoint of this study is the 6mSROT-50 (≥50x10⁹/L) rate at 6 months from treatment cessation. In patients with newly diagnosed primary immune thrombocytopenia

^b Listing for reconciliation should include all ICSRs submitted to Amgen Safety per contract (for studies in Table 2 listing should contain SUSARs, pregnancy and lactation exposure (and any associated reports/outcomes), USADEs, SADEs and non-serious ADEs).

treated with dexamethasone 40 daily x 4 days for one to three cycles, 6mSROT-50 (≥50x10⁹/L) at 6 months from treatment cessation has been assumed to be 30% [2]. The sample size was based on the assumption that ROM + DEX can improve sustained response at 6 months from treatment cessation up to 56.6% similarly to eltrombopag plus dexamethasone as described by Zhang [2]. A total of 63 patients/arm are required to achieve 80% power to detect a difference with a two-sided significance level of 5%, if the true 6mSROT-50 rates at 6 months from treatment cessation are 30% in the DEX arm and 56,6% in the ROM + DEX arm and assuming a dropout rate of 15%. The total minimal size is 126 patients to be randomized.

c. Analytical Populations

Safety Population

The safety population will consist of all randomized subjects who received at least one dose of study treatment. Subjects will be analysed according to the treatment actually received. Analysis for safety endpoints will use this analysis set.

ITT Population

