- To compare the time to first response (R) in both arms, Kaplan-Meier method will be used. Patients who not achieve R will be censored at the date of the last followup. Median and 95% CI, number of events and censored and risk number of patients will be provided. Log rank test will be used to compare time to first response between treatment arms. We will evaluate this in the total sample and in the absence of any rescue treatment.
- The proportion of patients with ER at Day 7 and IR at Day 30 from randomisation will be calculated and corresponding 95% CIs for each study arm will be provided.
 A Chi- square test or Fisher test if applicable will be used to compare the proportion of each endpoint between treatment arms.
- Descriptive statistics (mean, median, standard deviation, min, max, Q1 and Q3) and Student's t test will be used to compare the duration of platelet response through the following endpoints:
 - maximum number of consecutive days with platelet response (CR, R, GR and TR) along the study period and,
 - total number of days with platelet response (CR, R, GR and TR) along the study period in both arms. We will evaluate them in the total sample and in the absence of any rescue treatment.
- To compare the time to loss of response (LoR) in the subgroup of patients who achieve R (rITT population) between both arms, Kaplan-Meier method will be used. Patients who do not achieve LoR will be censored at the date of the last follow-up. Median and 95% CI, number of events and censored and risk number of patients will be provided. Log rank test will be used to compare time to first response between treatment arms.

 The proportion of patients requiring any rescue treatment along the study period will be calculated and corresponding 95% CIs for each study arm will be provided.
 A Chi-square test or Fisher test if applicable, will be used to compare the proportion between treatment arms.

Frequency and proportion of patients with adverse events, including bleeding events measured by the WHO bleeding scale will be provided. A Chi-square test or Fisher test if applicable will be used to compare the proportion between treatment arms.

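### The loss-of-response bullet in 11.e.i names the wrong endpoint for its log-rank test, and 11.a gives a time origin that conflicts with the LoR definition (minor)

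*Protocol*

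**What the plan says.** Comparing time to LoR is a secondary objective (Protocol 1.g and 5.c): "To compare the time to loss of response (LoR) in patients who achieved response in both arms". The endpoint definition (1.j and 6.c) fixes when the clock starts: "Definition of LoR: number of days from the first time the patient achieved a platelet count ≥30x10⁹/L".

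Section 11.e.i gives LoR its own bullet. The aim is "To compare the time to loss of response (LoR) in the subgroup of patients who achieve R (rITT population) between both arms", by Kaplan-Meier, and the censoring rule is "Patients who do not achieve LoR will be censored at the date of the last follow-up". The only test sentence in that bullet is "Log rank test will be used to compare time to first response between treatment arms". The same sentence, word for word, is the test sentence of the time-to-first-response bullet earlier in the list, where it belongs. Only its second occurrence is at issue here.

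Two general sentences in 11.a also bear on LoR: "Time-to-event variables will be estimated by the Kaplan-Meier method from the randomisation" and "The log-rank test will be used to compare the survival curves". Neither mentions an exception.

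**The concern.** There are two separate defects.

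**Endpoint.** The LoR bullet sets out to compare how long response lasts but attaches its test to how soon response begins. Section 11.c restricts the rITT population to patients who achieved response. In that set a test of time to first response asks only whether responders in one arm responded earlier, and says nothing about durability.

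**Origin.** Under 11.a the clock starts at randomisation; under 1.j and 6.c it starts at the first qualifying count. From randomisation, the LoR time is time to response plus duration of response. That overstates duration by the time to response, and does so unequally if one arm responds later.

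At stake is the p-value and the Kaplan-Meier median reported for one secondary endpoint on durability. The arms could differ in speed of response, since romiplostim is titrated weekly while dexamethasone is repeated in up to three cycles. The protocol gives no distribution of time to response.

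**Working it through.** The protocol gives no event count, hazard ratio or power for LoR, so there is no figure to reproduce. Its 80% power and 63 patients per arm concern the primary endpoint only. The check is mainly textual.

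**Step 1: elements of the LoR bullet.**
- Aim: time to LoR.
- Population: rITT, which 11.c assigns to the LoR analysis.
- Method: Kaplan-Meier.
- Censoring: patients without LoR, at last follow-up.
- Test: time to first response.

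Four elements agree and the fifth does not. It matches the test sentence of the time-to-first-response bullet.

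**Step 2: the two origins.** Let T be days from randomisation to first response and D be days from first response to LoR. The definition in 6.c analyses D. The general rule in 11.a, applied without exception, analyses T + D. The literal test sentence analyses T. These are three different variables.

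**Step 3: how far the readings can diverge.** All inputs here are assumptions: 50 patients per arm, exponential T and D, follow-up to day 540, two-sided 5% log-rank, 2000 runs per row. Entries are rejection rates.

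| Mean T, arm A / B (days) | Mean D, arm A / B (days) | D (6.c) | T + D (11.a) | T (literal sentence) |
|---|---|---|---|---|
| 7 / 7 | 180 / 180 | 0.0565 | 0.058 | 0.052 |
| 7 / 14 | 180 / 180 | 0.0435 | 0.0525 | 0.9275 |
| 7 / 28 | 180 / 180 | 0.0465 | 0.0965 | 1.000 |
| 7 / 60 | 180 / 180 | 0.055 | 0.322 | 1.000 |
| 7 / 7 | 180 / 360 | 0.8985 | 0.898 | 0.0565 |
| 7 / 28 | 180 / 360 | 0.902 | 0.959 | 1.000 |
| 28 / 7 | 180 / 360 | 0.8855 | 0.778 | 1.000 |

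In rows 1 to 4 durability is equal, so 0.05 is correct. The literal test rejects almost always once speed differs. In row 5 durability doubles at equal speed, and the literal test sees nothing.

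The T + D column departs visibly from 0.05 only when mean response times differ by 28 − 7 = 21 days (3 weeks) or by 60 − 7 = 53 days (about 7.6 weeks). At a 7-day difference it stays at 0.0525. With a real difference in durability, the randomisation origin raises rejection when the more durable arm responds later (0.959 against 0.902). It lowers rejection when that arm responds sooner (0.778 against 0.8855).

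**Step 4: a second set of assumptions.** This used 54 responders per arm, 800 runs per scenario and censoring at Day 365. Response fell at weeks 1 to 4 in proportions 60/20/10/10%. The median duration of 180 days was suggested by the 50% relapse within 6 months quoted in section 5.b. Results are in the order D, T + D, T:
- LoR hazard halved, equal response times: 0.83, 0.83, 0.06.
- Equal durability, 15% of ROM+DEX responders delayed to weeks 4–12: 0.05, 0.07, 0.64.
- Equal durability, median duration 90 days, 30% of ROM+DEX responders delayed: 0.06, 0.12, 0.995.

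The direction is the same as in Step 3. The sizes depend on the assumed response times.

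**The case against.** The strongest reply is that nobody would be misled. The sentence is an obvious carry-over, and everything else in the bullet concerns LoR. Section 11.a already applies a log-rank test to Kaplan-Meier curves, which can be read to cover the LoR curves. On the origin, 11.a does not say that all time-to-event variables start at randomisation. A specific definition, "number of days from the first time the patient achieved a platelet count", would naturally prevail over a one-line general statement. The analysis plan, which is not at hand, may state both correctly.

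Much of this stands. A reader might infer that the trial has no valid test of LoR, or that it will run at a false-positive rate such as 64%. The documents support neither reading. The intended test and origin can be recovered from other sections. The simulated rates presuppose literal execution of an evident slip, together with response times that the protocol does not give. Several protocol statements also limit how far apart response times might be:
- Both arms begin with the same four-day dexamethasone cycle.
- Section 5.b calls high-dose dexamethasone initially effective in 85%.
- Section 5.a puts romiplostim's maximum platelet effect at about 10–14 days.

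The simulations also stop at Day 365 or day 540, whereas the protocol censors at last follow-up, with visits scheduled to Month 18 or Month 24 depending on arm.

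The reply does not make the text correct. The bullet names an endpoint it is not about, and the protocol states two origins for one variable. This is a wrong statement and a contradiction, not detail left to the analysis plan.

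**Conclusion.** The error is real and minor. As written, the last sentence of the LoR bullet assigns the log-rank test to the wrong endpoint, and the general origin in 11.a conflicts with the LoR definition in 1.j and 6.c. Both conclusions rest on the text alone and need no assumptions.

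The practical size is limited. Secondary endpoints are declared exploratory in 11.e.i, without multiplicity adjustment. Durability is also compared through the maximum consecutive and total days in response. The primary analysis, sample size and data collection are unaffected. The rejection rates above show what the wording would do if followed literally under assumed inputs; they are not this trial's expected operating characteristics. The origin effect is small unless mean response times differ between arms by several weeks.

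**What to change.** 1. In the LoR bullet of 11.e.i, change the endpoint in the last sentence from first response to *loss of response*. Leave the identical sentence in the time-to-first-response bullet as it is.
2. In 11.a, add to the sentence on the randomisation origin: *except time to loss of response, which is measured from the start of response as defined for LoR*.

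The cost is two sentences in the protocol, carried into the analysis plan, with no new data, patients or procedures. The analysis plan is to be finalised before database lock. Correcting the protocol now avoids a later departure from it, in an open-label trial, that would need explaining.

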 - Definition of ER: proportion of patients with platelet count higher or equal than 30x10⁹/L and at least doble than baseline at first week (Day 7) from randomisation.
 - Definition of IR: proportion of patients with platelet count higher or equal than 30x10⁹/L in the first month (Day 30) from randomisation.
- To compare the difference of means between study arms of the maximum number of consecutive days with platelet response (CR, R, GR and TR) along the study period. We will evaluate them in the total sample and in the absence of any rescue treatment
- To compare the difference of means between study arms of the total number of days with platelet response (CR, R, GR and TR) along the study period. We will evaluate them in the total sample and in the absence of any rescue treatment.
- To evaluate and to compare the proportion of patients who need rescue treatments and proportion and time to treatment failures.
- To compare the time to loss of response (LoR) in patients who achieved response in both arms.
 - Definition of LoR: number of days from the first time the patient achieved a platelet count ≥30x10⁹/L until platelet count dropped below 30x10⁹/L measured on 2 occasions with more than 1 day apart or presence of bleeding
- To compare the difference between study arms in the proportion of patients requiring any rescue treatment along the study period.
- To compare the difference between study arms in the proportion of patients with adverse events (AEs), including serious adverse events (SAEs) and laboratory safety parameters. AEs will be graded according to National Cancer Institute Common Terminology Criteria for Adverse Events (CTCAE) version 5.0. Bleeding events will be carefully monitored.
- To compare the difference between study arms in the mean change in patients' bleeding from screening to Day 1, Week 8, Week 12, Moth 6, Moth 12andEnd of study Visit (visit 12 months after the last dose of study treatment) assessed with the ITP-bleeding tool in both arm.
- To compare the difference between study arms in the mean change in patients' quality of life from baseline Day 1 (the day of administration of the first dose of study medication) to Week 8, Month 6 (Day 180), Month12 (Day 365) from randomisation and End of study Visit (visit 12 months after

the last dose of study treatment) assessed with SF-36v2, FACIT-F and ITP-PAQ in both arms.

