Each subject who enters into the screening period for the study (when the subject signs the informed consent) will receive a unique subject identification number before any study-related activities/procedures are performed. The subject identification number will be assigned by the eCRF. This subject identification number will be used to identify the subject throughout the clinical study and must be used on all study documentation related to that subject.

Subjects who are determined not eligible after screening must be screen-failed in the eCRF and the reason for the screen failure provided.

Upon confirmation of eligibility, the site staff will use the eCRF to randomise a subject. Randomization of the patient is authorized until 72 hours after signing the informed consent. Randomization will be stratified by center with a 1:1 allocation using random block sizes to receive:

- Dexamethasone 40 mg daily x 4 days only in the first cycle and subcutaneous romiplostim weekly (ROM + DEX arm) for up to 12 months (365 days).
- Dexamethasone 40 mg daily x 4 days for up to 3 cycles every 14 to 28 days (DEX arm).

The investigator is responsible to document the decision to enroll the patient into the study and will note and date the information in the subject's medical record and in/on the enrolment CRF. Subjects will be considered enrolled upon randomization in the eCRF. The subject identification number must remain constant throughout the entire clinical study.

Romiplostim will be sent to the site upon subject screening.

d. Blinding procedures

Not applicable. Open label study.

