All patients who are randomized will be included in the ITT Population. The ITT Population will be used to summarize subject disposition and baseline characteristics. Patients will be analysed according to the treatment they were allocated to at randomization; not necessarily the treatment they actually received. Results will be presented "as randomized."

mITT Population

All patients who are randomized and received at least one dose of study medication will be included in the mITT Population. The mITT Population is the primary analysis population for efficacy. Patients will be analysed according to the treatment they were allocated to at randomization; not necessarily the treatment they actually received. Results will be presented "as randomized."

rITT Population

All patients who are randomized and received at least one dose of study medication and achieved response (R) at any time during the study will be included in the rITT Population. The rITT Population will be used for the analysis of time to loss of response. Patients will be analysed according to the treatment they were allocated to at randomization; not necessarily the treatment they actually received. Results will be presented "as randomized."

d. Analysis of Primary Objective

The primary endpoint is 6mSROT-50 rate at 6 months (180 days) from treatment cessation.

The proportion of patients with 6mSROT-50 and corresponding 95% CIs for each study arm will be provided. A Chi-square test or Fisher test if applicable, will be used to compare the proportion of 6mSROT-50 between treatment arms.

e. Analysis of Secondary Objectives

i. Secondary Efficacy evaluations

For the analysis of the secondary endpoints, following analyses will be conducted:

- The proportion of patients with 6mSROT-30, 12mSROT-30 and 12mSROT-50 and corresponding 95% CIs for each study arm will be provided. A Chi-square test or Fisher test if applicable will be used to compare the proportion of each endpoint between treatment arms.
- The proportion of patients with CR, R, GR or TR at 6 and 12 and End of study Visit (visit 12 months after the last dose of study treatment) will be calculated and corresponding 95% CIs for each study arm will be provided. A Chi-square test or Fisher test if applicable will be used to compare the proportion of each endpoint between treatment arms.

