- Quality of life measures using the SF-36 v2, FACIT-F and ITP-PAQ will be analysed. Change from baseline Day 1, (the day of administration of the first dose of study medication) to Week 8, Month6 (Day 180), Month12 (Day 365) and End of study Visit (visit 12 months after the last dose of study treatment) of SF-36 v2, FACIT-F and ITP-PAQ total score and each dimension score of SF-36 v2, FACIT-F and ITP-PAQ will be calculated. Both the change of scores and the scores at every assessed time point will be reported using the mean, median, standard deviation, min, max, Q1 and Q3.Student's t test will be used to compare the scores between treatment arms at different time points. Paired Student's t test will be used to evaluate the change from baseline at different time points within each treatment arm.
- The sum of all worst grades within each domain from the ITP-BAT questionnaire will be calculated and described at every assessed time point using the mean, median, standard deviation, min, max, Q1 and Q3.Student's t test will be used to compare the scores between treatment arms at different time points. Also, the change from baseline to Day 1, Week 8, Week 12, Month6 (Day 180), Month12 (Day 365) and End of study Visit (visit 12 months after the last dose of study treatment) of the sum of all worst grades within each domain from the ITP-BAT questionnaire will be calculated and described at every assessed time point using the mean, median, standard deviation, min, max, Q1 and Q3. Paired Student's t test will be used to evaluate the change from baseline at different time points within each treatment arm.
- Health resources use (HRU) associated with the ITP from treatment initiation (outpatient visits and home health care, hospitalizations and emergency visits, diagnostic procedures, pharmacological and non-pharmacological treatments and HRU related to of adverse drug reactions) and loss of productivity (number of days of absenteeism from school or work) will be summed up along the study and described using the mean, median, standard deviation, min, max, Q1 and Q3. Student's t test will be used to compare the scores between treatments.

In all hypothesis testing, p<0.05 will be considered statistically significant. No adjustments for multiplicity will be done. Since the amount of analysis of secondary objectives is numerous, results of the secondary endpoints should be considered exploratory and interpreted with caution.

ii. Secondary Safety evaluations

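### The stated QoL and ITP-BAT outcome is a between-arm difference in change from baseline, but Section 11.e.i names no between-arm test of change and leaves the baseline score unused

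*Protocol*

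**What the plan says.** Section 1.j defines the outcomes as contrasts of change, and Section 6.c repeats them. For quality of life: "To compare the difference between study arms in the mean change in patients' quality of life from baseline Day 1". For the ITP-BAT: "To compare the difference between study arms in the mean change in patients' bleeding from screening to Day 1". The baseline is therefore Day 1 for quality of life and screening for the ITP-BAT. Table 3 schedules both assessments.

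Section 11.e.i then sets the tests. For both groups of instruments a Student's "t test will be used to compare the scores between treatment arms at different time points". Changes from baseline are to be calculated and described. The only test attached to them is within arms: "Paired Student's t test will be used to evaluate the change from baseline at different time points within each treatment arm". No covariate appears in any of these comparisons.

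The same section makes no multiplicity adjustment and calls the secondary results exploratory. Section 11.a has a general sentence that promises appropriate tests for other endpoints, and says that the SAP will be finalised before database lock.

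**The concern.** The outcome sections promise one quantity and the analysis section tests two others. A between-arm test of follow-up scores ignores where each patient started. A paired test within an arm shows whether that arm moved, which may reflect natural course, regression to the mean or repeated measurement. A significant change in one arm and a non-significant change in the other does not show that the arms differ. Yet the protocol attaches its only tests of change to exactly that layout.

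Two things are at stake. The report could present within-arm p-values as the answer to a between-arm question, over four instruments and several visits each. And a baseline score that every patient is asked to provide would add nothing to the precision of the comparison.

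**Working it through.** **Plan's own figure.** The protocol gives no sample size or power for quality of life or the ITP-BAT. Its only calculation is for the primary endpoint (30% against 56.6%, two-sided 5%, 80% power, 15% dropout). It reproduces: 54 evaluable per arm by the pooled-variance formula, and 63 to 64 after inflation, against the stated 63. That figure is not in dispute; it supplies the sample sizes below.

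**Text side by side.**

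| | Stated outcome (1.j, 6.c) | Between-arm test (11.e.i) | Test of change (11.e.i) |
|---|---|---|---|
| QoL scales | between-arm difference in mean change from Day 1 | t test on scores | paired, within arm |
| ITP-BAT | between-arm difference in mean change from screening | t test on scores | paired, within arm |

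In the ITP-BAT bullet the between-arm t test comes first and change is introduced after it, with only the paired test attached. That bullet cannot be read as a between-arm test of change.

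**Cost in precision.** Assume equal variance (set to 1) at baseline and follow-up, and correlation r between them. The protocol gives no r, so 0.3, 0.5 and 0.7 are assumptions. The variance that enters the between-arm comparison is:

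- follow-up score (as planned): 1
- unadjusted change: 2(1 − r)
- baseline-adjusted (ANCOVA): 1 − r²

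Fix the true difference where the planned test has 80% power: (1.960 + 0.842) × √(2/n). This is 0.50 SD at n = 63 per arm, and 0.54 SD at n = 53 (63 × 0.85, rounded down). With variance V, power is about Φ(2.802/√V − 1.960), which is the same at either n.

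| r | V, change | V, ANCOVA | Power, planned | Power, change | Power, ANCOVA | Gain in effective patients, 1/(1 − r²) − 1 |
|---|---|---|---|---|---|---|
| 0.3 | 1.40 | 0.91 | 80% | 66% | 84% | 10% |
| 0.5 | 1.00 | 0.75 | 80% | 80% | 90% | 33% |
| 0.7 | 0.60 | 0.51 | 80% | 95% | 98% | 96% |

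Worked line for r = 0.5: 2.802/√0.75 = 3.235; 3.235 − 1.960 = 1.275; Φ(1.275) = 0.90.

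So replacing scores by unadjusted change would match the wording but lose power when r is below 0.5. Baseline adjustment is at least as precise as either alternative at every r shown. With the baseline as covariate, the treatment coefficient is the same whether the response is the score or the change, so it also matches the stated outcome.

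**The case against.** The strongest reply is that the objective is in fact tested. With 1:1 randomisation and a baseline unaffected by allocation, the expected between-arm difference in follow-up score equals the expected difference in change. The planned t test is therefore valid for the same null hypothesis. This stands. A reader might infer that the objective goes unanswered or that the test is biased; the documents do not support that.

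Second, the quality-of-life bullet mentions both change and scores just before the t test, so scores might be meant to cover both. That is arguable for quality of life, but the ITP-BAT bullet does not allow it. The general sentence in 11.a names no method and does not displace tests that 11.e.i names. The SAP could add an adjusted model, but the protocol itself fixes these tests.

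Third, the endpoints are unpowered and exploratory. That stands and limits the severity.

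A reader might also extend the point to the primary endpoint, because "Randomization will be stratified by center with a 1:1 allocation using random block sizes to receive" the two regimens while "A Chi-square test or Fisher test if applicable, will be used to compare the proportion of 6mSROT-50 between treatment arms" without stratification. The check does not support a defect there. In 3,000 simulated trials per setting (126 patients, 30 centres, no dropout, assumed between-centre SD of 0, 0.5 and 1.0 on the logit scale), type I error was:

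- unstratified chi-square: 4.7%, 4.2% and 3.7%
- centre-stratified Cochran-Mantel-Haenszel test: 4.7%, 4.9% and 5.3%

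Power was 86.5%, 83.6% and 73.2% against 84.2%, 82.4% and 76.0%. There is no inflation, and power moves by about −2 to +3 points. Centres average 126/30 = 4.2 patients, which is sparse for stratification. Country is not the stratification factor, and no gain from it has been computed. Covariate adjustment of the primary test is a matter for the SAP.

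**Conclusion.** The point holds as an internal mismatch with a modest cost. The stated outcome for three quality-of-life instruments and the ITP-BAT is a between-arm difference in change. The protocol names no between-arm test of change and tests change only within arms.

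The planned between-arm test is valid but less efficient than it need be. Baseline-adjusted variance is 0.91 to 0.51 of the planned variance, and power rises from 80% to between 84% and 98%. These figures rest on an assumed r of 0.3 to 0.7, equal variances at the two times, complete data, and one r applied to all instruments. At the low end the gain is small. The mismatch in the text does not depend on any of these assumptions.

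The primary analysis is not at fault on this ground. A 95% CI for the risk difference in 6mSROT-50 would be a sensible addition to 11.d, but its absence is not an error in the plan.

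**What to change.** In Section 11.e.i, for SF-36v2, FACIT-F, ITP-PAQ and ITP-BAT:

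- Replace the unadjusted between-arm t test by an ANCOVA at each time point, or an MMRM over visits, of change or score, with arm and the baseline score as terms.
- Name the baseline for each instrument: Day 1 for quality of life, screening for the ITP-BAT. The ITP-BAT bullet now lists change from baseline to Day 1 without saying that baseline is screening.
- Report the adjusted between-arm difference with its 95% CI at each time point.
- Label the within-arm paired tests descriptive, and state that they are not used to judge a difference between arms.

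Optionally, add to 11.d a 95% CI for the risk difference in 6mSROT-50.

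The cost is a few sentences. The baseline scores are already scheduled, and visits and sample size do not change. Section 13.d requires an amendment for any change to the protocol, so the edit can go with the next one, and the SAP should carry the same wording before database lock.
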